Study procedure	
After verification of eligibility criteria, parents will be randomly web-based randomization to either the BEM group intervention or the control group intervention. If both parents are eligible, they will be allocated to the same study arm.
 
Randomization will be stratified by study center.
 
Upon obtaining informed consent, parents will receive login credentials for the study's web platform, through which they will complete the required questionnaires. At enrollment, socio-demographic data of the parents and clinical data related to the child/adolescent will also be collected.
 
Parents will then be invited to participate in either the BEM group intervention or the standard group intervention. Both group activities will be conducted under the supervision of trained healthcare personnel and will have the same duration, although their content will differ.
 
(Non-specialized healthcare personnel will receive specific training in a two-day weekend course (8 hours per day) led by professionals experienced in the BEM methodology).
 
Specifically, the BEM group will receive basic information on diabetes management using external resources (medical support, technology, telemedicine, carbohydrate counting techniques) and internal resources (learning effective techniques and behaviors to improve metabolic control). This will be followed by the experiential BEM-specific program.
 
The control group will receive the same diabetes management information, combined with opportunities for parent discussion and recreational activities.
 
Each group activity will include 25 parent participants.

	At 3 and 6 months following the group intervention, parents will be asked to complete the same questionnaires again via the web platform. Glycemic data for the children/adolescents will be retrieved from electronic medical records.

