Statistical aspects	
Sample Size Estimation
 
 - The difference between the two groups in changes in PSI-SF scores (primary endpoint) will be expressed in terms of effect size (i.e., the difference in mean scores between groups divided by the common standard deviation at baseline). An effect size of at least 0.5 is widely accepted in the literature as clinically relevant. In a previous study [13], baseline PSI-SF scores were 75.4 ± 2.5, indicating that an effect size of 0.5 corresponds to a between-group difference of 1.25. To detect an effect size of at least 0.5 with 80% statistical power ($\alpha = 0.05$), a minimum of 64 parents per group is required. Assuming a dropout rate of 15%, a total of 150 parents (75 per group) will be enrolled. 
Data Analysis
 
 - Descriptive statistics will be reported as mean and standard deviation or, in the case of non-normally distributed continuous variables, as median and interquartile range. Categorical variables will be reported as percentages. - Between-group comparisons for descriptive variables will be conducted using the Student's t-test or the Mann-Whitney U test for continuous variables, and the chi-square test for categorical variables. - Comparisons between study arms will be performed using Mixed Models for Repeated Measures (MMRM), including the baseline value of the outcome as a linear covariate and study arm as a fixed effect. MMRMs account for both within-subject and between-subject correlations using a first-order autoregressive (AR(1)) variance-covariance structure. Similarly, comparisons between study arms for secondary endpoints, including questionnaire scores and glycemic metrics (change from baseline at 3 and 6 months), will also be conducted using MMRMs. These models will include baseline values of the respective outcomes as linear covariates and the study arm as a fixed effect. Results will be reported as estimated means with corresponding 95% confidence intervals. - Subgroup analyses will also be conducted based on parental sex and child/adolescent age (<10 years vs. ≥ 10 years).
Participating Sites	Participation is planned for six pediatric diabetes centers. Enrollment will be competitive.
Ethics aspects	The study protocol will be submitted for approval to the Ethics Committees of the participating centers.

KEY ROLES AND CONTACTS

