4.3 Procedures for assigning interventions in the study

4.3.1 Randomization procedure

After verification of the eligibility criteria, the parents will be assigned via centralized web-based randomization to participate in either the BEM group activity or the control group (1:1 randomization). In cases where both parents are eligible, they will be allocated to the same study arm. The randomization will be stratified by center.

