5.2 Description of the control method

In the control group, basic information on diabetes management will be provided through external resources (medical support, technology, telemedicine, carbohydrate counting techniques) and internal resources (learning effective techniques and behaviors to improve metabolic control). The control group will receive the same diabetes management information, accompanied by parent discussion sessions and recreational activities guided by the diabetes team staff. As with the BEM group, activities will take place over three days in an off-hospital location, in contact with nature. Each group activity will involve 25 parents.

STUDY PROCEDURES

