7.2 Statistical Analysis

All subjects enrolled in the study will be included in the analysis.

Descriptive data will be expressed as means and standard deviations or as medians and interquartile ranges for continuous variables, and as percentages for categorical variables.

Group comparisons for descriptive variables will be performed using Student's t-test or the Mann-Whitney U test for continuous variables, and the chi-square test for categorical variables.

Regarding the primary endpoint (difference in PSI-SF scores at 3 months compared to baseline), the comparison between study arms will be conducted using mixed-effects models for repeated measures (MMRM), which will include the baseline outcome value as a linear covariate and the study arm as a fixed effect. MMRM accounts for within- and between-subject correlations through a variance-covariance matrix with an autoregressive order 1 structure.

Similarly, comparisons between study arms for secondary endpoints related to questionnaire scores and glucometric measures (differences at 3 and 6 months compared to baseline) will be performed using MMRM.

These models will include the baseline value of the respective outcomes as a linear covariate and the study arm as a fixed effect. Results will be expressed as estimated means with 95% confidence intervals.

In addition to the analysis of the entire sample, subgroup analyses will be conducted separately based on parent sex and children/adolescents' age (<10 years and ≥ 10 years).

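### Randomisation is stratified by centre but the stated MMRMs omit centre; with balanced allocation and a prognostic centre, this alone makes the reported standard error too large

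*Protocol*

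**What the plan says.** **Allocation.** Protocol section 4.3.1 states: "The randomization will be stratified by center". The synopsis (Study procedure) repeats it: "Randomization will be stratified by study center". The ratio is 1:1; no block size or balancing method is given. Section 3.1 plans six centres, and the synopsis (Participating Sites) adds "Enrollment will be competitive", so centre sizes are not fixed.

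**Analysis.** The model terms are named three times:
- section 7.2, primary endpoint: "which will include the baseline outcome value as a linear covariate and the study arm as a fixed effect";
- section 7.2, secondary endpoints: "These models will include the baseline value of the respective outcomes as a linear covariate and the study arm as a fixed effect";
- synopsis, Statistical aspects: "including the baseline value of the outcome as a linear covariate and study arm as a fixed effect".

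Centre is in none of these, as a fixed or a random effect. The AR(1) structure is described only for correlation within and between subjects, so it does not bring centre in.

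**Two design features that act the other way.** Section 4.3.1 says of couples: "In cases where both parents are eligible, they will be allocated to the same study arm". Section 5.2 says of delivery: "Each group activity will involve 25 parents".

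**The concern.** Stratifying by centre pays off in precision only if the analysis uses the factor. Two conditions decide whether leaving it out harms the reported standard error:

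1. allocation is balanced within centre, for example by permuted blocks;
2. centre predicts the outcome after adjustment for baseline.

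When both hold, centre differences cancel from the arm contrast but stay in the residual variance of a model without centre. Confidence intervals are then wider, and power lower, than the design supports, for the primary and all quantitative secondary comparisons. The point estimate is unaffected and its sampling variation hardly changes. If either condition fails, this omission does not miscalibrate the standard error.

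**Working it through.** **The plan's own figure.** For an effect size of 0.5, two-sided alpha 0.05 and 80% power (section 7.1), the exact t-test gives 64 per arm (power 0.8015), as stated. With 15% dropout, 64/0.85 = 75.3, so 76 per arm or 152 in total. The stated 150 leaves 75 × 0.85 = 63.75 per arm. The sample size reproduces within rounding.

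**Assumed inputs.** The documents give no centre variance, so the share ρ of the baseline-adjusted residual variance that lies between centres is set at 0.05, 0.10 and 0.20. Also assumed are the centre sizes 32/28/24/20/14/10 (128 evaluable parents), a baseline–outcome correlation of 0.5 and, for power, an effect of 0.5 SD.

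**Formula.** Let σ² be the residual variance after baseline adjustment and w the fraction of parents in each centre.
- With exact balance within centre, the true variance of the arm difference is (4/N)σ²(1−ρ).
- A model without centre estimates the residual variance as about σ²(1−ρΣw²).
- The ratio of reported to true SE is therefore √[(1−ρΣw²)/(1−ρ)].

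Here Σw² = (1024+784+576+400+196+100)/16384 = 0.188.
- ρ = 0.05: √(0.9906/0.95) = 1.021
- ρ = 0.10: √(0.9812/0.90) = 1.044
- ρ = 0.20: √(0.9624/0.80) = 1.097

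The actual two-sided error, 2[1−Φ(1.96 × ratio)], is then about 4.5%, 4.1% and 3.2%. With many small centres Σw² tends to 0, and the ratio rises to 1/√(1−ρ): 1.026, 1.054 and 1.118.

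**Simulation, independent parents, single visit.** Permuted blocks of 2, 4 or 8 within centre, 20,000 trials per cell (Monte Carlo SE about 0.15 points at 5%):

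| ρ | SE too large by | Type I error without centre | Type I error with centre | Power lost (points) |
|---|---|---|---|---|
| 0.05 | 1–2% | 4.5–4.8% | 4.9–5.2% | 0.6–0.7 |
| 0.10 | 3–4% | 4.0–4.3% | 5.0–5.2% | 1.3 |
| 0.20 | 9–10% | 3.2–3.5% | 4.9–5.2% | 2.4–2.6 |

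At ρ = 0 with blocks of 4, both models have 89.7% power.

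**Two-visit AR(1) MMRM.** With 150 randomised, blocks of 4, 15% missing at 3 months and 20% at 6 months, true residual correlation 0.6, and visit and arm-by-visit terms, the 3-month SE is 1.2%, 2.9% and 7.4% too large. Power lost is 0.6, 1.2 and 2.7 points.

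**Effect set at 0.5 of the residual SD.** This puts power near 80% rather than 90%. Power without and with centre is 0.803 and 0.814, 0.812 and 0.831, and 0.834 and 0.873: losses of 1.1, 1.9 and 3.9 points.

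**Unrestricted 1:1 allocation within centre.** Type I error without centre is 4.9–5.2%, so there is no conservatism. Adding centre changes power by −1.3 points at ρ = 0, then by −0.2, +1.3 and +3.8.

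**Couples in one arm.** With 30–80% of parents in couples, within-family correlation 0.3–0.5 and ρ from 0.05 to 0.20, type I error is:
- 4.2–9.8% for the model as stated;
- 5.8–10.5% with centre alone added;
- 4.7–5.7% with centre and a family term.

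With a family term in both models, centre adds 0.7–1.2, 1.9–2.8 and 3.9–6.0 power points.

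**Groups of 25.** If the activity group carries an assumed variance share of 0.01, 0.02 or 0.05, type I error with centre and family in the model is still 6.8–7.7%, 10.0–10.2% or 15.0–17.1%.

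**Child glycaemic outcomes.** Two parents of one child carry identical values. Keeping both rows gives type I error of 6.5–14.0% as stated and 8.8–15.7% with centre. One record per child gives 3.0–4.8% without centre and 4.9–5.3% with it, and centre then adds 0.9–1.1, 1.7–2.8 and 3.7–6.1 power points.

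**The case against.** **The list of terms may be open.** Section 7.2 says what the models contain, not that they contain nothing else. It also omits visit, which the separate 3- and 6-month comparisons require and which the two-visit simulation above supplies. A SAP could add centre in the same way. This part stands: the omission may already be repaired elsewhere. But visit is implied by the comparisons the protocol asks for, and nothing in the text implies centre. The protocol chose to name covariates in three places and each time left out its one stratification factor. A SAP that follows the wording would omit it too.

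**Neither condition is established.** This is correct. No block method or centre variance is given, and under unrestricted allocation adding centre costs a little power at low centre shares. The point is therefore conditional.

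**The loss is small and depends on the baseline correlation.** This is also correct. In a further run with 5,000 trials per cell, losses at ρ = 0.05, 0.10 and 0.20 were about 0.9, 2.6 and 4.3 points at correlation 0, 0.7, 1.4 and 2.5 at 0.5, and 0, 0.4 and 0.6 at 0.7. The SE ratio does not depend on this correlation, because ρ is defined after baseline adjustment.

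**Clustering by family and activity group matters more.** It can, and it pushes the other way. For that reason the overall test is not called conservative here, and centre should not be added alone.

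**Conclusion.** The concern holds. The trial randomises by centre and names models that ignore it. With balance within centre and a centre effect that survives baseline adjustment, the omission by itself overstates the SE by about 1–2%, 3–4% or 9–10% at residual centre shares of 0.05, 0.10 or 0.20. It costs roughly half a point to four points of power in most of the settings examined, and almost nothing when baseline correlation is high. All these inputs are assumptions.

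There is no bias and no inflation of type I error from this source. The net calibration of the test is a separate matter: shared allocation of couples and delivery in groups can make the reported SE too small. The change is worth making because it is nearly free, but the trial does not fail without it. Confidence in the size is medium.

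**What to change.** In section 7.2 and the synopsis:
- Add centre as a fixed effect to the primary and secondary MMRMs. Because enrolment is competitive, set a rule for pooling very small centres before database lock.
- For parent-reported outcomes, pair centre with an allowance for within-family correlation: a family random intercept or family-clustered standard errors. Centre alone is not safe when couples enrol.
- For child glycaemic outcomes, analyse one record per child with centre in the model. A family intercept is degenerate there.
- Do not describe this as restoring nominal error, since effects of the activity groups remain uncovered.

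**Cost.** One or two sentences and about five degrees of freedom (six centres less one). With blocked allocation this costs essentially no power if centre is not prognostic; with unrestricted allocation, about 1.3 points. A coded centre and a coded family or child identifier must reach the analysis file. Centre is already needed for randomisation and section 11 describes a pseudonymised eCRF, so this should be feasible. It should be confirmed before lock, because section 5.4 treats the questionnaires as anonymous and section 11 says the analysed database is anonymised.

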5.3 Procedures

All parents of participating children will be offered the opportunity to participate in the study and will be asked to sign an informed consent form during a routine visit of their child. After verifying eligibility criteria and obtaining informed consent, parents will be randomly assigned via a centralized web-based randomization process to either participate in the BEM group activity or to the control group. If both parents are eligible, they will be allocated to the same study arm.

Once consent to participate has been obtained, parents will receive login credentials for the study's web platform, through which they will be able to complete the required questionnaires. Socio-demographic information of the parents and clinical data related to the child/adolescent will also be collected at enrollment.

Parents will then be invited to participate in either the BEM group activity or the standard activity. At 3 and 6 months after the group activity, parents will be asked to complete the questionnaires again via access to the portal. The glycemic data of the children/adolescents will be derived from continuous glucose monitoring (CGM) measurements and extracted from the electronic medical records provided by the participating diabetes centers.

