It should be noted that the instruments used in this study are intended for epidemiological and screening purposes and are not to be considered diagnostic tools. Furthermore, the questionnaires are anonymous, as they are completed directly through a dedicated online platform accessed via personal login credentials. Therefore, the researchers will not have access to individual scores. However, if pathological scores are identified, the participant will be informed and, if necessary, referred to specialized services.

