7 STATISTICAL CONSIDERATIONS

7.1 Sample Size Calculation

The primary endpoint is the PSI-SF questionnaire score at 3 months after the completion of group activities. The primary efficacy assessment will therefore involve comparing the differences in PSI-SF scores at 3 months relative to baseline between the study arms.

The difference between the two groups in changes of PSI-SF scores will be expressed in terms of effect size (the difference in scores between the two groups divided by the common standard deviation at baseline). It is widely accepted in the literature that an effect size of at least 0.5 can be considered clinically relevant [27]. From the previous study [13], baseline PSI-SF values were 75.4 ± 2.5 ; therefore, an effect size of 0.5 would correspond to a difference of 1.25 between groups.

To detect an effect size of at least 0.5 with a statistical power of 80% ($\alpha=0.05$), at least 64 parents per group need to be evaluated. Assuming a dropout rate of 15%, a total of 150 parents will be enrolled (75 per group)

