11 DATA COLLECTION

The medical history and data of children with T1D, who are the offspring of study participants, will be extracted from their medical records and recorded on a pseudonymized eCRF. At study entry, the following information regarding the child will be collected: sex, age, level of education, ethnicity, body weight, height, duration of diabetes, diabetes treatment, presence of diabetes-related complications, last HbA1c value, glucometric data from continuous glucose monitoring (TIR, TAR, TBR), presence of other chronic conditions, hospitalizations in the past year due to severe hypoglycemia, diabetic ketoacidosis, or other reasons, participation in school camps, and engagement in physical activity. The medical records will serve as source documents for these data.

The data required by the protocol will be entered into an electronic case report form (eCRF). The quality and completeness of the data will be verified during and after data collection.

Regarding the parents, the collected data will include age, education level, employment status, marital status (married or cohabiting, separated, divorced, widowed, single/celibate), number of children, household size, and presence of other family members with diabetes. These details will be directly recorded by the parents through personalized access to the dedicated web platform used for the study, which will also facilitate questionnaire completion.

Throughout and at the end of the study, a database review will be performed to monitor data quality and completeness. Any modifications will be tracked using audit trail systems. Once all queries are resolved, the database will be frozen. The database will then be archived and subjected to backup and storage policies in accordance with GCP guidelines, and made available for subsequent audits if required. Raw data will be stored in a database for statistical analysis, which will be conducted after database lock. The impact of missing data on the primary endpoint will be assessed, and the need for imputation techniques will be considered.

An anonymized database will be managed and analyzed at the Center for Outcomes Research and Clinical Epidemiology (CORESEARCH s.r.l.) in Pescara.

12 Publication Policy

All analysis results will be produced solely and exclusively in aggregated form and in a manner that is not attributable, either directly or indirectly, to any individual patient.

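### Parents of the same child are allocated together, but the sample size treats parents as independent and the AR(1) matrix is wrongly said to cover between-subject correlation

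*Protocol*

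**What the plan says.** Section 4.3.1 states: "In cases where both parents are eligible, they will be allocated to the same study arm". The synopsis (Study procedure) and sections 3 and 5.3 repeat the rule. Section 4.3.1 adds: "The randomization will be stratified by center".

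Section 7.2 analyses all enrolled subjects. It compares arms with an MMRM whose named terms are the baseline score and the study arm, and says of correlation that "MMRM accounts for within- and between-subject correlations through a variance-covariance matrix with an autoregressive order 1 structure". The synopsis (Statistical aspects) makes the same claim: "MMRMs account for both within-subject and between-subject correlations using a first-order autoregressive (AR(1)) variance-covariance structure". The protocol mentions no family effect, family covariance block or clustered standard error, and no rule limiting the analysis to one parent per child.

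Section 7.1 derives the sample size from a standardised effect of 0.5, 80% power and alpha 0.05, concluding that "at least 64 parents per group need to be evaluated". It gives no expected share of couples and no couple correlation.

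**The concern.** An AR(1) matrix describes how correlation decays across ordered visits of one subject, here 3 and 6 months. It says nothing about two different subjects, who remain independent in the model. The protocol therefore states that between-subject dependence is dealt with, by a device that cannot deal with it.

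The dependence arises from the design. Two parents rate their stress about the same child and always share an arm. If their baseline-adjusted PSI-SF scores correlate positively, a model that ignores this overstates the information in the data. Standard errors, intervals and p-values for the primary endpoint are then too optimistic. A reader of section 7.2 would believe that couples are already covered.

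**Working it through.** **Reproducing the stated figure.** Two-sample t-test, d = 0.5, two-sided alpha 0.05: the required n is 63.8, so 64 per arm, with power 80.1%. At 15% dropout, 75 × 0.85 = 63.75. So 64 is the figure for independent individuals, with no allowance for couples.

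**Assumed inputs.** Let p be the share of analysed parents who belong to an enrolled couple, ICC the within-couple correlation of the baseline-adjusted score, and r the baseline-to-follow-up correlation. The protocol gives none of these, nor the share of variance due to centre.

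**Formulas.**
- Design effect: DE = 1 + p × ICC
- Effective n per arm: 64 / DE
- Understatement of the SE: 1 − 1/√DE
- Type I error when couples are ignored: 2 × (1 − Φ(1.96/√DE))
- Power with correct SEs: noncentral t at n = 64 / (DE × (1 − r²)), assuming equal SD at baseline and follow-up
- Baseline correlation that restores 80% power: r = √(1 − 1/DE)

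| p, ICC | DE | Effective n per arm | SE too small by | Type I error | Power, r = 0 | Power, r = 0.5 | Break-even r |
|---|---|---|---|---|---|---|---|
| 0.3, 0.2 | 1.06 | 60 | 2.9% | 5.7% | 78% | 88% | 0.24 |
| 0.5, 0.3 | 1.15 | 56 | 6.7% | 6.8% | 74% | 86% | 0.36 |
| 0.7, 0.5 | 1.35 | 47 | 13.9% | 9.2% | 67% | 80% | 0.51 |

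The power columns describe an analysis with correct standard errors. With p = 0 or ICC = 0, nothing changes.

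**Does baseline adjustment repair the type I error?** No. A simulated ANCOVA of the 3-month score on baseline and arm (64 per arm, 20,000 runs, no true effect) rejected in 5.2% of runs with no couples, 6.9% at (p, ICC) = (0.5, 0.3), 8.3% at (1, 0.3) and 10.9% at (1, 0.5).

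**Does omitting centre cancel it?** Randomisation is stratified by centre but the model names no centre term, which makes standard errors too large if centres differ. Simulation: 128 evaluable parents, families allocated 1:1 within six centres, outcome taken as the baseline-adjusted score, arm-only model, no true effect, 80,000 runs per cell, Monte Carlo error about ±0.2 points.

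| p, ICC | Type I error, centre share 0 | Type I error, centre share 0.10 |
|---|---|---|
| 0.1, 0.3 | 5.2% | 4.5% |
| 0.3, 0.2 | 5.6% | 4.9% |
| 0.5, 0.3 | 6.7% | 5.8% |
| 0.7, 0.5 | 9.3% | 8.0% |

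Family-clustered standard errors on the same data gave 5.0% to 5.2% at centre share 0 and about 4.2% at 0.10.

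**The case against.** The protocol never names the unit within which the covariance matrix is blocked, and a family effect or sandwich standard error could sit in a statistical analysis plan that is not shown. That is fair for the choice of technique. It does not rescue the sentence, which fixes a method and credits it with something it cannot do. An analysis plan that followed it would carry the error forward.

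The size of the effect rests wholly on assumptions. Baseline adjustment may already remove some lasting similarity between partners, and both parents must be willing to attend and complete questionnaires, so couples may be few. With few or weakly correlated couples and some centre variation, the error is negligible (4.5% and 4.9% above). This stands. However, the offset from omitting centre is accidental, and it fails when couples are common and strongly correlated (8.0%).

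The sample size part is the weaker one. At r = 0.5 the power is about 80% or more across the whole range, so no larger sample is called for.

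Parent records must already be linked to the child, since subgroups by the child's age are planned, so keeping a family key should not be hard. That is also fair, and lowers the cost of the fix.

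Finally, the simulations include no effect of the activity groups of 25 parents (75/25 = 3 per arm). They do not show that family clustering is all this trial needs; that is a separate question.

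**Conclusion.** The point holds. The AR(1) claim is wrong as written in both section 7.2 and the synopsis, whatever the data turn out to be. Its consequence is conditional: zero without couples or couple correlation, and in the opposite direction if that correlation is negative. For assumed couple shares of 0.3 to 0.7 and correlations of 0.2 to 0.5, the type I error of the primary test is about 5.7% to 9.2% with no centre effect, and about 4.9% to 8.0% in simulation if centre carries 10% of the variance. The stated 80% power depends on the same unknowns in both directions: couples lower it, and the baseline covariate, which section 7.1 does not credit, raises it. It should be corrected before analysis, but it does not call the design or the enrolment target into question.

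**What to change.** In section 7.2 and the synopsis:
- Account for family in every parent-level model, including the primary one, by a family random effect, a family-level covariance block or family-clustered standard errors. The last is the safer choice if few couples enrol.
- Limit the AR(1) sentence to the repeated visits of one parent.
- Carry a pseudonymised family identifier into the analysis file.

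In section 7.1, keep 150 parents and state the power as conditional on a named couple share, couple ICC and baseline correlation. Clustering by activity group can be added as an optional sensitivity analysis.

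The cost is wording plus data linkage. The randomisation system must already know which parents belong together. But section 5.4 says that "the questionnaires are anonymous", and section 11 says "An anonymized database will be managed and analyzed" and lists no family identifier among the parent data. The privacy wording therefore needs checking so that the link is not lost.

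The statistical price is a primary interval wider by √DE − 1, about 3% to 16% for DE 1.06 to 1.35, possibly a less favourable stated power, and a slightly conservative test (about 4.2%) if centre matters and stays out of the model.

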6.2 Frequency of endpoint assessment

Study questionnaires will be completed at baseline (randomization) and at 3 and 6 months following participation in group activities. The primary endpoint will be the comparison between study arms of the difference in PSI-SF questionnaire scores at 3 months post-participation relative to baseline. Clinical parameters (glycemic indices) will be recorded with the same frequency (baseline, 3 and 6 months), and the values considered will be those from the two weeks preceding baseline and follow-up at 3 and 6 months.

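### AR(1) over two follow-up visits only adds an equal-variance restriction, which can misstate the 3-month standard error once the model is made visit-specific, as the primary endpoint needs

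*Protocol*

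**What the plan says.** Section 7.2 specifies a mixed model for repeated measures for the PSI-SF change at 3 months, "which will include the baseline outcome value as a linear covariate and the study arm as a fixed effect". No visit term and no arm-by-visit term is listed. The covariance is "a variance-covariance matrix with an autoregressive order 1 structure"; the synopsis (Statistical aspects, Data Analysis) repeats this as "using a first-order autoregressive (AR(1)) variance-covariance structure". Neither place gives a heterogeneous version, a fallback structure or a robust standard error. Both say that this structure takes care of correlation between subjects as well as within them.

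Section 6.2 sets the schedule: "Study questionnaires will be completed at baseline (randomization) and at 3 and 6 months following participation in group activities". It defines the primary endpoint as "the comparison between study arms of the difference in PSI-SF questionnaire scores at 3 months post-participation relative to baseline". The same model form is used for the secondary questionnaire and glycaemic endpoints at 3 and 6 months.

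The only spread reported for PSI-SF is at baseline (section 7.1: "baseline PSI-SF values were 75.4 ± 2.5"). No SD is given for 3 or 6 months.

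**The concern.** AR(1) is useful when there are several visits and correlation fades with distance in time. Here baseline is on the right-hand side of the model, which leaves two outcomes and one correlation, so there is no decay to describe. Compared with a free 2x2 matrix, AR(1) does one thing: it sets the 3- and 6-month variances equal.

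The primary question is about 3 months. If the model is fitted with a separate arm effect at each visit and the usual model-based standard errors, the 3-month SE is built from a variance pooled over both visits. If spread is smaller at 6 months, the 3-month SE is too small and the test is anti-conservative. If spread is larger at 6 months, the SE is too large and power is lost.

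The statement about between-subject correlation is a second problem, and it needs no assumption about variances. A visit matrix within each parent treats different parents as independent. That matters for how the sentence is read, because two eligible parents of one child go to the same arm (sections 3 and 4.3.1) and each activity is delivered to a group of 25 parents (section 5.2 and synopsis).

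**Working it through.** **Inputs from the protocol.** 64 evaluable parents per arm, effect size 0.5, 80% power, alpha 0.05 (section 7.1); 1:1 allocation (section 4.3.1); two post-baseline visits (section 6.2).

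**Assumptions.** r = residual SD at 6 months / residual SD at 3 months, taken from 0.8 to 1.25; complete data; independent parents; correlation 0.6 between visits in the simulations; two-sided test. The effect of 0.5 is in units of the 3-month residual SD, whereas section 7.1 scales it by the baseline SD.

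**The plan's own figure.** An exact two-sided t-test with effect size 0.5 has power 0.8015 at 64 per arm and 0.795 at 63, so 64 reproduces. For dropout, 128/0.85 = 150.6 against the stated 150, which is close enough.

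**Visit-specific model.** With arm-by-visit means and complete data, the 3-month estimate is the plain difference in 3-month means (baseline adjustment aside). With the 3-month SD set to 1, its true SE is sqrt(2/64) = 0.177. Under AR(1) the variance used is (1 + r²)/2, so

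model SE / true SE = k = sqrt((1 + r²)/2).

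In the normal approximation, type I error is 2 × [1 − Φ(1.96k)] and power is Φ(0.5/0.177 − 1.96k) = Φ(2.83 − 1.96k). The simulated columns come from 40,000 trials per setting with 64 per arm.

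| r | k | Type I, formula | Type I, simulated | Power, formula | Power, simulated |
|---|---|---|---|---|---|
| 0.8 | 0.906 | 7.6% | 7.7% | 85.4% | 85% |
| 0.9 | 0.951 | 6.2% | 6.2% | 83.2% | 82.5% |
| 1.0 | 1.000 | 5.0% | 4.7% | 80.7% | 79.8% |
| 1.1 | 1.051 | 3.9% | 3.8% | 77.9% | 77.5% |
| 1.2 | 1.105 | 3.0% | – | 74.7% | 74.0% |
| 1.25 | 1.132 | – | 2.7% | – | 72% |

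With a separate variance per visit, simulated type I error was 4.8% to 5.1% and power 79.7% to 80.4% at every simulated r from 0.8 to 1.25. A small run (1,500 trials, r = 0.8, 10% missing at 6 months) gave mean SEs of 0.1617 under AR(1) and 0.1769 unstructured. Their ratio, 0.914, is close to the 0.906 above. Its null rejection rates were 5.5% and 3.5%. They differ in the expected direction, but the run is too small to fix either level.

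**Model as literally listed (baseline and arm only).** With complete data, AR(1) gives both visits equal weight, so the arm effect is the 3/6-month average. At r = 0.8 and correlation 0.6 the covariance is 0.6 × 0.8 = 0.48. The true variance of the averaged outcome is (1 + 0.64 + 2 × 0.48)/4 = 0.65. The AR(1) version is (0.82 + 0.48)/2 = 0.65, where 0.82 = (1 + 0.64)/2. They agree, so the SE is not distorted. Simulation confirms this: SE 0.142 against 0.143 at r = 0.8, and 0.178 against 0.178 to 0.179 at r = 1.25, with type I error 5.1% to 5.2%.

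**Changing only the covariance in the arm-only model.** Generalised least squares then weights the visits by the inverse covariance. At r = 0.8 the weights are proportional to 0.64 − 0.48 = 0.16 (3 months) and 1 − 0.48 = 0.52 (6 months), so 3 months gets 0.16/0.68 = 24%. At r = 1.2 the covariance is 0.72, the weights are 1.44 − 0.72 = 0.72 and 1 − 0.72 = 0.28, and 3 months gets 72%. The quantity estimated would depend on the variance ratio.

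**The case against.** The strongest reply is that the protocol does not write down the model in which the harm occurs. It lists arm as the only fixed effect besides baseline, and under that model the SE is correct whatever r is. Section 7.2 also does not say that 6-month scores enter the primary model; if 3 months is analysed alone, AR(1) has nothing to act on. This stands. A reader might infer that the 3-month error bars are wrong whenever the two variances differ, and the document does not support that: it takes an arm-by-visit model and model-based SEs as well. But neither escape rescues AR(1). The averaged effect is not the endpoint in section 6.2, and in a single-visit analysis the structure is idle.

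The second reply is that nothing in the protocol suggests unequal variances. This also stands. A reader might go to r = 0.7 and cite a type I error of about 9%, but that needs the residual variance to halve between the visits (0.7² = 0.49). For r above 1 the test is conservative, so only power suffers. With complete data the point estimate does not move.

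The third reply is that robust SEs or fallback structures may be in an analysis plan not shown here. Their absence from the protocol is no fault, and a robust SE would repair the standard error with AR(1) kept. AR(1) itself, however, is fixed in the protocol with no exception.

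Lastly, an unstructured visit matrix does not handle correlation between parents either. The nominal error rates shown for it hold only for independent parents.

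**Conclusion.** The point holds in conditional form. With two post-baseline visits, AR(1) is compound symmetry, and its only added content is an equal-variance restriction that nothing in the protocol supports. In a visit-specific model with model-based SEs, the 3-month SE is off by sqrt((1 + r²)/2): about 5% for a 10% SD difference and about 10% for a 20% difference, with the error rates tabulated above. If the SDs are equal there is no effect. The size rests on r, which is assumed, and on complete data and independent parents.

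Under the fixed effects as listed the SE is sound, but the estimate is the 3/6-month average. The missing visit and arm-by-visit terms are therefore the larger defect of the same specification. A reader might infer that replacing AR(1) alone is enough; the weights above show that, in the arm-only model, this can move the estimate further from 3 months.

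The claim that this matrix accounts for between-subject correlation is wrong as written, whatever r is. The sample size calculation is not affected by this point.

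**What to change.** In section 7.2 and in the synopsis (Statistical aspects, Data Analysis), make these changes together:

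- Specify arm, visit (3 and 6 months) and arm-by-visit as fixed effects, with the baseline value as covariate.
- Name the arm contrast at 3 months from this model as the primary test; the 6-month contrast is secondary.
- Replace AR(1) with an unstructured 2x2 covariance for the two visits, for the primary and secondary models. Do not make this change without the two changes above.
- Remove the statement that the matrix accounts for between-subject correlation. Removal corrects the text but supplies no term for parents of the same child or in the same group; whether to model those is a separate decision.

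The cost is a few words in two places and one more covariance parameter (three instead of two), which is negligible with 128 evaluable parents. The planned 64 per arm and 150 in total do not change.
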